## 8.12 Patient Withdrawal or Discontinuation

If a patient is withdrawn from the clinical study, the reason for withdrawal shall be recorded on the Study Exit eCRF and in the patient's medical record.

Possible reasons for withdrawal from the study are:

- Adverse Event;
- Patient withdrew consent;
- Investigator withdrew patient from the study for medical reasons;
- Investigator withdrew patient from the study due to inclusion/exclusion criteria not met.

No patient follow-up is scheduled as per study design (excluding resolution of ongoing adverse events). Patients withdrawn for reasons other than screen failure will not be replaced.

Withdrawn patients will be treated according to standard clinical practice.

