#### 4.1.2. Secondary Objectives and Endpoints

The study secondary objectives are the followings:

1. To compare the two study Phases (see Section 5) in terms of primary endpoint incidence.
2. To compare the two study Phases in terms of respiratory AEs and SAE incidence, number of ICU transfers and related length of stay, Code blues and RRT responses.
3. To evaluate the impact of introducing continuous monitoring devices connected to a remote monitoring platform on the clinical workflow, defined as the rate of clinical early interventions performed by nursing staff to prevent a potential AE (e.g. patient stimulation, Jaw thrust maneuver, oxygen administration started or increased, medication change, etc.).

4. To evaluate the impact of introducing continuous monitoring devices connected to a remote monitoring platform on clinical staff workflow, defined as clinical staffs' satisfaction related to the monitoring system.
5. To characterize the predictive values of etCO2, RR, SpO2, plethysmography-derived RR, IPI and EWS in respect to respiratory AEs and other SAE.

Related secondary endpoints are:

1. Incidence of RC markers recorded by the monitoring system during each Phase.
2. Incidence of respiratory AEs and SAE, number of ICU transfers and related length of stay, Code blues and RRT responses recorded in the two study Phases.
3. Average rate of early interventions for patient will be calculated in both study Phases. In Phase I there should only be non-alarm-triggered interventions, as in clinical practice, while in Phase II there should be two sub-groups of clinical early interventions: alarm-triggered and non-alarm-triggered.
4. Clinical staff's satisfaction related to the monitoring system's introduction in their current workflow will be evaluated through a survey performed at the end of the study.
5. Sensitivity and specificity of each monitored parameter in predicting and identifying respiratory AEs and SAE will be calculated. EWS will be the only parameter not automatically collected by the monitoring system but manually collected.

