## 8. Study Procedures

### 8.1 Schedule of Events

Data will be collected for Screening, Enrollment Visit and Monitoring Period. Additional data will be collected for Adverse Events, Device Deficiencies and Protocol Deviations.

Data collection requirements are summarized in Table 2. The study site personnel must report all study specific Adverse Events and changes in status of these Adverse Events from time of enrollment until a patient exits the study.

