## 8.8 Study Exit

Once the monitoring period has ended the patient will be treated according to the hospital clinical practice. The patient will exit the study upon their discharge from the hospital. Any adverse events (as defined in section 10) observed between the end of the monitoring period and study exit are reportable (as described in section 10.2). The Study Exit eCRF will be used to document that the patient has exited from the study. The reason for study exit will be captured on the Study Exit eCRF. The date of study exit, which should correspond to the date of discharge from the hospital will also be captured here.

If the study exit was for any reason other than normal study completion, refer to section 8.12 of the CIP, for appropriate Study Exit eCRF completion.

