**Table 3 - Protocol Deviation by Reason - FAS**

**Table 4 - Protocol Deviation by Visit - FAS**

**Listing 1 - Other deviations – FAS**

### 7.1.3. Analysis Sets

The following patient sets will be used for the analysis:

- The Full Analysis Set (FAS) includes all patients actively enrolled in the study, who signed Informed Consent Form (ICF), fulfilled the inclusion/exclusion criteria and monitored by CS20p or PM1000N. The FAS will be used to describe both baseline characteristics and safety outcomes of the study population;
- The Per Protocol Set (PPS) includes all patients in the FAS, without major protocol deviations, who have at least 24 hours of monitoring *effective time*. The PPS will be used to describe baseline characteristics of the study population and to evaluate the primary and secondary endpoints. Patient with poor quality of device data, defined as having less than 90% of time continuously monitored, will be included or excluded from the PPS, as appropriate.

The following table shows how each population set will be used for analyses:

Population set	Baseline assessment	Primary and Secondary Endpoint #1	Secondary Endpoints #2, #3, #4 and #5	Safety AE Death
FAS	✓		✓	✓
PPS	✓	✓	✓	

For those patients who have less than 24 hours or poor quality of device data monitoring or who withdrew, the analyses will include all data up to the point of their last data collection only for FAS population.

An additional set could be created during the analysis phase, in case necessary to investigate on a particular subgroup of patients.

 Effective time is the cumulative time with valid recorded data. This aimed to filter out periods of time where the patient was not connected to the Capnography cannula or pulse-ox sensor, but recording was on-going (the patient was not monitored during this time).

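### A patient withdrawn for an adverse event or medical reasons is not followed to discharge for new secondary endpoint #2 events, so later ICU transfers, Code blues, RRT responses and SAEs can be missed

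*Protocol*

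**What the plan says.** Protocol 8.12 introduces a list with "Possible reasons for withdrawal from the study are". An adverse event comes first, and an investigator's decision on medical grounds is a separate item. Both are reasons for leaving the study. The section goes on: "No patient follow-up is scheduled as per study design (excluding resolution of ongoing adverse events", and "Withdrawn patients will be treated according to standard clinical practice". It says nothing about continuing to record study outcomes.

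The normal route is different. Protocol 8.8 states: "The patient will exit the study upon their discharge from the hospital". Events between the end of monitoring and that exit are reportable. For other exits it says: "If the study exit was for any reason other than normal study completion, refer to section 8.12 of the CIP". Protocol 8.1 requires sites to report study-specific adverse events and "changes in status of these Adverse Events from time of enrollment until a patient exits the study".

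Secondary endpoint #2 (Protocol 4.1.2) covers respiratory AEs and SAEs, together with "number of ICU transfers and related length of stay, Code blues and RRT responses recorded in the two study Phases". SAP 7.9.2 compares the phases on incidence by chi-square or Fisher's exact test, and adds Poisson rates if exposure differs. For patients with short or poor-quality monitoring "or who withdrew, the analyses will include all data up to the point of their last data collection", a rule that SAP 7.1.3 restricts to the Full Analysis Set (FAS). Protocol 12.3 plans no imputation; SAP 7.4 leaves a later choice of method open.

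**The concern.** How long a patient is observed for endpoint #2 can depend on how that patient is doing. An uncomplicated patient is observed to discharge. A patient withdrawn because of an adverse event or a medical decision may be observed for new events only up to the withdrawal. Such patients are plausibly at higher risk of further events than the rest, so the missing time is unlikely to be a random sample of patient time.

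Endpoint #2 is where the study compares clinical events between blinded and alarmed monitoring. If withdrawals for these reasons are not equally frequent in the two phases, or are followed by events at different rates, the difference enters the comparison. Correcting the normal end of observation would not close this gap, because it lies in the early-exit route.

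**Working it through.** **1. The plan's own allowance.** SAP 6 starts from 182 evaluable subjects and allows 10% for withdrawal or dropout and 5% for monitoring attrition.
- 182 × 1.15 = 209.3
- 182 × 1.10 × 1.05 = 210.2
- 182 / (0.90 × 0.95) = 212.9

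The stated total of about 210 is reproduced. (Protocol 12.1 still prints 260, and 260 × 1.15 = 299; that is a separate matter.) The 10% is for all withdrawals: 0.10 × 70 = 7 in Phase I and 0.10 × 140 = 14 in Phase II. Neither document says how many would be for adverse events or medical reasons.

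**2. The two routes compared.**
- *End of study participation.* Normal route: hospital discharge (Protocol 8.8). Withdrawal: date of withdrawal (8.12).
- *New AE or SAE afterwards.* Normal route: reportable between end of monitoring and discharge (8.8). Withdrawal: after exit, so outside the window in 8.1.
- *Event already ongoing.* Withdrawal: followed to resolution (8.12), with outcome and resolution date recorded (10.2).
- *Death.* Reportable on either route; Protocol 10.3 sets no time limit.
- *ICU stay, Code blue, RRT response.* Transfers within the hospital are recorded on the Monitoring eCRF (8.7). None of the three is a minimum adverse event item in 10.2 or a named row in Protocol Table 2. Following an ongoing event to resolution therefore does not guarantee that they are captured.

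**3. Which parts of endpoint #2 are exposed.** A patient withdrawn for a respiratory AE or an SAE already counts in that incidence, because the event precedes exit. What can be missed is a later ICU transfer, Code blue, RRT response or further SAE, and part of an ICU stay. A patient withdrawn on medical grounds without a reportable event is exposed on every component.

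**4. Whether the analysis corrects it.** In the chi-square or Fisher comparison, an FAS patient with no recorded event of a given type counts as not having had one, however short the observation. The Poisson rates, if reported, use exposure ending at study exit (SAP 7.7). That adjusts for shorter time only if exit is unrelated to later risk. The Per Protocol Set, also used for endpoint #2, requires 24 hours of effective monitoring, so a patient withdrawn earlier drops out of it.

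**5. Scale (assumptions, not figures from the plan).** Let w be the share of a phase withdrawn for an adverse event or medical reasons, and q the share of those who later have a first event of a given type that goes unrecorded. The incidence of that type is understated by w × q. Take w from 2% to 10% (the upper end assigns the whole withdrawal allowance to these reasons) and q from 10% to 50%.
- Lowest: 0.02 × 0.10 = 0.2 percentage points, or 0.14 patients in Phase I and 0.28 in Phase II.
- Highest: 0.10 × 0.50 = 5.0 percentage points, or 3.5 patients in Phase I and 7.0 in Phase II.
- One missed patient: 1/70 = 1.4 percentage points in Phase I; 1/140 = 0.7 in Phase II.
- Unequal phases: with q = 30%, w = 2% in one phase and 10% in the other gives 0.6 and 3.0 points, an error of 2.4 points in the difference. Its sign depends on which phase has more withdrawals.

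**The case against.** The case on the other side is substantial.

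- **Deaths.** A reader might infer that deaths after withdrawal are lost. The documents do not support that. Protocol 10.3 requires every patient death to be reported and sets no time limit, and a fatal outcome of an ongoing event falls within follow-up to resolution. The end of reporting at exit in 8.1 leaves deaths from a new cause after exit somewhat unclear, but no more than that.
- **Worsening of the same event.** Protocol 8.12 keeps ongoing events in follow-up, and Table 4 requires new information on an already reported SAE to be sent to the sponsor immediately. Respiratory insufficiency that later leads to ICU transfer is therefore at least partly covered. This stands; the remaining gap is new events and the details of ICU stay.
- **Withdrawal is optional.** The reasons in 8.12 are possible ones. Nothing makes ICU transfer or removal of a sensor an exit, and 8.8 already treats the end of monitoring as different from the end of the study. An investigator could stop monitoring and keep the patient in. This stands too: the loss is a risk, not a certainty. However, 8.12 does not tell sites to prefer that course.
- **Withdrawn patients stay in the FAS.** They do, and the last data collection in SAP 7.1.3 is not defined as the exit date. Keeping the patient in the denominator does not supply events that nobody was asked to record.
- **Bias in favour of alarms.** A reader might infer that alarmed monitoring would look safer than it is. Nothing in the documents says that alarms change the rate of formal withdrawal, and an earlier ICU transfer in Phase II would itself be counted. The direction is unknown.

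**Conclusion.** The gap is real but narrow. Under Protocol 8.1, 8.8 and 8.12 read together, new endpoint #2 events after withdrawal for an adverse event or medical reasons are not required to be collected, while other patients are observed to discharge. ICU length of stay may also be incomplete. The loss would be informative, and neither the incidence tests nor the rates in SAP 7.9.2 remove it.

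The size cannot be derived. Under the ranges assumed above it runs from 0.2 to 5.0 percentage points per phase. Two larger-looking figures should not be used as losses. The first is 21 patients (10% of 210), which is the allowance for all withdrawals and counts patients, not missed events. The second is about 2.7 deaths (210 × 1.286%, the predicted mortality at POSPOM 24). It applies one threshold score to everyone, although entry is by POSPOM or ARISCAT, and deaths are reportable in any case.

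The conclusion takes Protocol 8.8 as governing normal exit, consistent with the version 2.0 change to discharge. Protocol 5 and 5.1 and SAP 5.1 still describe participation as ending with monitoring or at 72 hours at most, and need to be reconciled with it. The primary endpoint, which comes from device data, is not affected by this point. It is a cheap improvement.

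**What to change.** 1. In Protocol 8.12, distinguish *monitoring stopped* from *withdrawn from study*, without prescribing when monitoring should stop.
2. For every eligible patient who has not withdrawn consent to data collection, keep recording the endpoint #2 items from the hospital record to discharge: respiratory AEs, SAEs, ICU admission and discharge times, Code blues and RRT responses. Patients found ineligible need not be included, since Protocol 12.3 removes them from the FAS.
3. In SAP 7.1.3 and 7.9.2, state that these data enter the FAS analysis of endpoint #2, and that last data collection for this endpoint means discharge, or withdrawal of consent if earlier.
4. Report the number and timing of adverse event and medical withdrawals by phase, so that a reader can judge whether the loss could differ.

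The cost is a protocol amendment, with ethics committee submission as Protocol 14.6 requires, and a small amount of extra data entry for a few patients from records the site already holds. No visits or procedures are added.

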## 9. Risks and Benefits

### 9.1 Potential Risks

Devices used in this clinical study are commercially available and Medtronic is not aware of any concerns with these products. In the clinical study, the products will be used in accordance with their labeling, therefore no risks other than the risks typically associated with routine device use are anticipated.

Risks will be minimized by careful assessment by the patient's doctor prior to, during, and after the monitoring phase. In addition, apart from the monitoring, patients are treated according to general clinical practice, so no extra tests or follow-ups are required for the study. Therefore, no additional risks are associated with participation in this clinical study.

Possible risks associated with Capnostream™ 20p or Nellcor monitoring is mild to moderate skin irritation or discomfort (redness, itching, rash, pressure) associated with the pulse oximetry sensor or related to the application or removal of the sensor. The skin will be assessed before and after the application of the pulse oximetry sensors. Patients with known skin contact allergies to medical grade adhesives will not be recruited.

Possible risks associated only with Capnostream™ 20p is mild to moderate skin irritation or discomfort involved in wearing a filterline similar to a supplemental O2 tube with an added oral scoop to collect a gas sample near the mouth for CO2 analysis. The design mitigation to reduce skin allergic reactions is the use of latex free, ISO 10993 compliant components. Design of the oral/nasal interface and low pump suction pressure for sampling are means to reduce risk of discomfort.

### 9.2 Potential Benefits

Patients' participation in this study may offer no additional benefit in respect to the same treatments provided outside of the study.

Possible benefits for participating in this study include the following (although others are possible):

- Study patients may benefit from the structured, well-controlled clinical surveillance provided during the monitoring phase.
- The information gained from this study could result in the improved post-surgical management of other patients. Additionally, information collected from this study may assist in the design of a subsequent outcome study, the design of new product(s)/therap(y/ies) and/or instructions for use.

### 9.3 Risk-Benefit Rationale

Medtronic believes that the potential risks associated with the conduct of this study are minimal, using non-significant risk, non-invasive study devices for the following reasons:

- All the devices used in the study are commercially available and used within their intended use.
- Additional surveillance will be provided for close monitoring and recording of the patients' clinical status.

## 10. Adverse Events and Device Deficiencies

In this study the following AEs will be collected:

- All AEs with an underlying respiratory cause
- All SAEs
- All adverse device effects (ADE)

In addition, device deficiencies (DD) will be collected for this study.

RC markers will not be considered AE if the patient is asymptomatic and no actions are taken.

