Respiratory compromise (RC) is a state in which there is a high likelihood of decompensation into respiratory depression, respiratory failure or death, but in which specific interventions (enhanced monitoring and/or therapies) might prevent or mitigate decompensation. Patients with RC have up to a two-fold increase in mortality following delayed medical emergency team activation. Detecting a patient's declining RC status before progression to respiratory depression in patients continuously monitored in the general ward could allow earlier intervention, thus potentially decreasing adverse outcomes.

Due to possibly improved patient safety, continuous SpO2 and capnography monitoring combined with automated decision support tools to determine potential or established patient critical illness are starting to have an important role also outside ICU. Current standard of care for respiratory monitoring of high risk hospital ward patients, such as those receiving opioid therapy, is intermittent documentation of SpO2 value (e.g. spot checks performed at 4 to 6 hours intervals). Respiratory rate (RR) is often determined by clinician assessment though manual inaccurate respiration counts.

Growing evidence supports the use of capnography for earlier and more reliable warnings of potential RC in postoperative patients in the general ward, compared with pulse oximetry. Capnography monitoring has also been associated with in-hospital mortality in emergency department patients with cardiac arrest and suspected sepsis across a range of disease severity.

There are no data on the real incidence and severity of potential RC markers and their correlation with cardiopulmonary or other complications in European postsurgical patients. A pilot study on this topic could be useful to collect information on the utility of continuous SpO2 and capnography monitoring in this setting and to develop future clinical evidence. This study may also provide the data needed to evaluate certain health-economic outcomes associated with introduction of continuous monitoring in the general ward setting.

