## 8.7 Monitoring Period

Continuous monitoring from either Capnostream™ 20p or Nellcor Monitoring Systems will be performed on all patients for a minimum of 24 hours. The monitoring period will last up to patient's full mobilization or up to a maximum of 72 hours, if the patient is still bed-ridden after two days post-surgery.

The monitoring period will start for patients once they arrive on the ward. For patients who are determined to be at high risk due to opioid therapy and not due to other pre-existing factors, monitoring of capnography and pulse oximeter data will start only after opioid therapy has been initiated.

Monitoring may be discontinued if the patient is discharged from the hospital ward.

During Phase I the alarm feature of the monitoring devices will be silenced and the screen information blinded. A regular check during the monitoring period should be completed to ensure the etCO2 filter line and SpO2 sensors are appropriately fitted on the patient.

During Phase II the medical staff will be instructed to respond to alarm feature of the monitoring devices and their screen will be open. A guideline will be created to instruct the nurses in responding to alarms and changes in the monitored parameters. An alarm will be considered a false positive by the observer if the SpO2 sensor or the etCO2 filter line is off the patient or misplaced. Alarms will be considered true positive if the SpO2 sensor and etCO2 filter line placement is correct: observations on patient activity and subsequent interventions will be recorded in the eCRF to identify clinically significant or insignificant alarmed events. As an example, patient activities such as talking, eating or gripping a book with the SpO2 sensor compressed will be marked as true positive with details of the activity recorded to identify the alarmed event as potentially clinically insignificant if no medical intervention was taken. The Monitoring eCRF will be completed to document:

- Care pathway (location/transfer within hospital)
- Alarm threshold applied to the monitor (to be collected during the Monitoring Phase II only for each measured parameter, PR, RR, SpO2 and EtO2).
- Systolic blood pressure and level of consciousness using the AVPU scale to allow the retrospective NEWS analysis
- Monitoring duration
- Vital signs
- Supplemental oxygen use
- Medications
- Product information

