## 16. Appendices

### Appendix A: List of Anticipated Adverse Events

In Table 5 a list of possible respiratory related adverse events occurring in high risk post-surgical patients is reported.

In Table 6 a list of device related adverse events that may be possibly caused by the use of the devices required by this protocol is reported.

Note that occurrence of RC markers alone, if patient is asymptomatic and no invasive actions are taken, are not considered as adverse events but would meet the primary endpoint definition.

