### 7.9.2. Secondary Endpoints

The secondary endpoints are:

1. To compare phases in terms of Primary endpoint incidence;
2. To compare phases in terms of respiratory and SAE incidence, number of ICU transfers and related length of stay, Code blues and RRT responses.
3. To evaluate the rate of clinical early interventions performed by nurse staff to prevent a potential AE, introducing continuous monitoring devices connected to a remote monitoring platform;
4. To evaluate the nurses’ satisfaction related to the monitoring system introducing continuous monitoring devices connected to a remote monitoring platform;
5. To establish the Predictive values of  $\text{EtCO}_2$ , RR,  $\text{SpO}_2$ , plethysmography-derived RR, IPI and EWS in respect to respiratory and other SAE.

In order to evaluate secondary **endpoints #1 and #2**, the incidence of events will be reported together with the comparison between phases, by means of the Chi-square test or Fisher exact test for extreme

proportions, as appropriate. If the monitoring/study exposure results different between phases, also the rates of events will be reported, together with the 95% Poisson Confidence Intervals. The Poisson regression model will be used to calculate the Incidence Rate ratio (IRR), with the d-scale option.

For **endpoint #3**, the rate of clinical early interventions will be calculated as (number of early interventions)/(total time-person in FAS) and it will be reported together with the 95% Poisson Confidence Interval.

Early interventions include, as defined in CRF (Monitoring Period):

1. Stimulated subject to breathe;
2. Repositioned/opened airway;
3. Held or reduced Respiratory Depressive (RD);
4. Added or increased supplemental oxygen;
5. Ventilation support;
6. Other

**Endpoint #4** will be evaluated reporting a summary of the nurses' satisfaction answers.

To identify the predictive values for EtCO2, RR, SpO2, plethysmography-derived RR, IPI and EWS, which can predict respiratory and other SAE, a sensitivity analysis will be performed (**endpoint #5**), and the following parameters will be reported, for each RC marker:

1. **Sensitivity** = 
$$\frac{(\# \text{ of clinical events "Yes" and with RC marker "Yes"})}{(\# \text{ of clinical events "Yes"})} = \frac{TP}{(TP+FN)}$$
2. **PPV** = 
$$\frac{(\# \text{ of clinical events "Yes" and with RC marker "Yes"})}{(\# \text{ of events with RC marker "Yes"})} = \frac{TP}{(TP+FP)}$$

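### Two conflicting rules decide when an RC marker is exempt from being an adverse event, and one of them makes the Phase I v Phase II comparison of respiratory AEs depend on alarm responses

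*Protocol*

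**What the plan says.** Protocol section 10 sets the exemption in these words: "RC markers will not be considered AE if the patient is asymptomatic and no actions are taken". Appendix A, which introduces the anticipated events, words it differently: "Note that occurrence of RC markers alone, if patient is asymptomatic and no invasive actions are taken, are not considered as adverse events". Neither passage refers to the other. SAP sections 7.9.2 and 7.10, which analyse and tabulate adverse events, do not choose between them.

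The phases differ in whether staff can see a marker. Protocol section 8.7 says "During Phase I the alarm feature of the monitoring devices will be silenced and the screen information blinded", and then "During Phase II the medical staff will be instructed to respond to alarm feature of the monitoring devices and their screen will be open". Protocol section 4.1.2 draws the consequence for actions: "In Phase I there should only be non-alarm-triggered interventions, as in clinical practice", while Phase II has both alarm-triggered and other interventions.

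The affected endpoint is secondary endpoint 2 in protocol section 4.1.2: "Incidence of respiratory AEs and SAE, number of ICU transfers and related length of stay", with Code blues and RRT responses, recorded in the two phases. SAP section 7.9.2 compares its incidence between phases by chi-square or Fisher exact test, at the two-sided 0.05 level of section 7.2. The same section lists the early interventions to be recorded. Several are non-invasive, for example "Added or increased supplemental oxygen".

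**The concern.** An outcome compared between two phases should be counted the same way in both. Under section 10, whether a marker in an asymptomatic patient stays exempt depends on whether somebody acted on it. Prompting staff to act is what Phase II introduces, so the intervention under study can alter the count as well as the patients' condition.

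A rise in respiratory AEs in Phase II could then reflect more bedside responses and no additional harm. A true benefit could be masked for the same reason. Under Appendix A, non-invasive responses would not have this effect. The result of a planned safety comparison could therefore turn on which of two passages was applied. If that choice is made after the data are seen, it will not be credible.

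**Working it through.** **1. The two rules side by side.** For an asymptomatic patient with an RC marker:

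| What follows the marker | Section 10 | Appendix A |
|---|---|---|
| No action | exempt | exempt |
| Non-invasive action (stimulation, repositioning, oxygen) | not exempt | exempt |
| Invasive action | not exempt | not exempt |

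They conflict in the middle row only. Several of the early interventions listed in SAP section 7.9.2 fall in that row.

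**2. Dependence on phase.** In Phase I an action on a marker must come from ordinary observation. The protocol background describes current practice as "spot checks performed at 4 to 6 hours intervals". In Phase II staff are told to respond to alarms, and the recommended settings in Appendix B trigger after 30 seconds. Actions occur in both phases, but alarm-triggered ones only in Phase II.

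**3. Size of the spurious gap.** The documents give no AE rate under either rule, so there is no planned figure to reproduce. Let b be the proportion with a respiratory AE whatever the rule, m the proportion with an asymptomatic marker, and q the chance that any action follows. Assume that every non-exempt marker is reported as an AE. Then under section 10:

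- phase incidence = b + (1 − b) × m × q
- gap between phases = (1 − b) × m × (q₂ − q₁)

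If q is equal in both phases, the gap is zero. The documents do not give q.

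Illustration at 70 v 140 with the same b and m in both phases. The values b = 2% and 3.4% are borrowed from complication rates in protocol section 3.1, and their use as AE rates is an assumption. The 37% is that section's figure for prolonged desaturation. For b = 2%, m = 10%, q = 0.1 v 0.5:

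- Phase I: 0.02 + 0.98 × 0.10 × 0.1 = 3.0%
- Phase II: 0.02 + 0.98 × 0.10 × 0.5 = 6.9%

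| m | q Phase I v II | Phase I (b = 2% to 3.4%) | Phase II (b = 2% to 3.4%) | Fisher test rejects |
|---|---|---|---|---|
| 10% | 0.1 v 0.5 | 3.0–4.4% | 6.9–8.2% | 12–13% |
| 20% | 0.1 v 0.8 | 4.0–5.3% | 17.7–18.9% | 79–85% |
| 37% | 0.3 v 0.8 | 12.9–14.1% | 31.0–32.0% | 81–84% |

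With q = 0.1 in both phases, Fisher rejects in about 3%, below the nominal 5%.

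**4. False rejection for a given gap.** The SAP's evaluable number, 182, is consistent with its enrolment: 182 × 1.15 = 209.3, about 210. (The 260 in protocol section 12.1 is not, since 260 × 1.15 = 299. That is a separate matter.) Split 1:2, 182 gives about 61 v 121, taken here as 60 v 120. With 10% assumed in Phase I and no true difference, exact binomial calculation gives:

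| Spurious gap (points) | Chi-square, 60 v 120 | Fisher, 60 v 120 | Chi-square, 70 v 140 |
|---|---|---|---|
| 0 | 5% | 3% | 5% |
| 5 | 14% | 11% | 15% |
| 10 | 40% | 36% | 45% |
| 15 | 70% | 67% | 77% |
| 20 | 90% | 88% | 94% |

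**5. What those gaps require.** Rearranging step 3 with b = 10%, m = gap / (0.9 × (q₂ − q₁)). With q₂ − q₁ = 0.7:

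- 5 points: 0.05 / 0.63 = 7.9%
- 10 points: 0.10 / 0.63 = 15.9%
- 15 points: 0.15 / 0.63 = 23.8%
- 20 points: 0.20 / 0.63 = 31.7%

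The plan's 10% is a minimum marker proportion. At exactly 10%, gaps of 15 or 20 points are impossible. A gap of 10 would need an action for every marker in Phase II, none in Phase I, and no overlap with other AEs.

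**The case against.** A reader might infer that respiratory AE incidence is inflated in Phase II by definition. The documents do not support that, for four reasons.

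- Section 10 is an exclusion. It says when a marker is not an AE, not that a marker followed by an action is one. The investigator still applies the ISO definition and confirms the respiratory nature of the event (section 10.2). This stands. However, that definition covers untoward clinical signs, so a site could reasonably report a non-exempt desaturation.
- Actions are expected in Phase I too, so only the difference in action rates matters, and it is not given. Earlier intervention could also lower true AEs in Phase II. This stands: the expected bias is upward, but the net observed direction is open.
- If Appendix A governs, the mechanism largely disappears. The anticipated respiratory AEs in Table 5 fit that reading, since they list airway support, ventilation, ICU transfer, arrest and death but not stimulation or added oxygen. Nothing says that Appendix A governs, though, and an alarm-triggered invasive action would count under it as well.
- The 40% to 90% figures rest on an assumed base rate and large gaps. A 5-point gap gives about 14%.

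It is also fair to say that this is a secondary comparison in a pilot sized for precision of the primary endpoint. ICU transfers, Code blues and RRT responses do not use the rule, and cross-site assessment (section 11) reduces the scope for each site to read it differently. AE records hold the time and the actions taken. These points limit the damage. They do not tell the assessors which rule to apply.

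**Conclusion.** The concern holds in a limited form. Section 10 and Appendix A contradict each other for an asymptomatic marker followed by a non-invasive action, and nothing in the protocol or SAP resolves it. Under section 10, AE ascertainment depends on phase, so the between-phase comparison of respiratory AEs in secondary endpoint 2 carries an expected upward bias in Phase II.

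The size of that bias cannot be derived from the documents. Depending on assumed marker prevalence and action rates, the chance of a false difference runs from modest (about 12% to 14%) to high (80% or more). All these figures assume no true difference and that every non-exempt marker is reported as an AE. The contradiction and the dependence on phase are read directly from the text and rest on none of the assumed rates.

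**What to change.** Reconcile section 10 and Appendix A into one rule, and state in the SAP which rule feeds endpoint 2. Keep safety reporting complete. For endpoint 2:

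- Base the between-phase AE comparison on symptomatic respiratory AEs and on SAEs.
- Include Table 5 events but flag those that were alarm-triggered. Several are themselves defined by an action, such as ventilation support or transfer to the ICU, so they are not free of the same dependence.
- Report asymptomatic episodes of marker plus non-invasive action separately under endpoint 3, split by alarm-triggered or not.
- Add a sensitivity analysis of endpoint 2 that counts those separated episodes.

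This lessens the dependence on phase but does not remove it, since alarms may also help staff notice symptoms.

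The cost is wording in both documents and a little extra analysis. The data are already planned: interventions by relation to alarms (protocol Table 2), action taken in response to an alarm (section 8.7), and event time and actions in each AE record (section 10.2). Phase II AE counts in endpoint 2 may be lower as a result.
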